9.3.2.1 Definition of Headache, Migraine, and Probable Migraine Days

A headache day is determined by the recording in the electronic diary of headache specific characteristics and/or symptoms for a calendar day. In general, the duration of headache must be at least █ hours that day in order to be analyzed as a headache day, but this definition might be altered for some sensitivity analyses (to █ hours or █ minutes, for example). The duration constraint is removed if an acute headache medication is taken that day.

A migraine day is a headache day of at least █ hours duration containing at least one set of headache characteristics and symptoms that fit the following definition of a migraine,

where a "set" refers to headache data reported for the same diary report. The four migraine characteristics are (1) unilateral location (rather than bilateral), (2) pulsating/throbbing quality (rather than pressing/squeezing), (3) moderate or severe pain intensity (rather than mild) and (4) aggravated by or causing avoidance of routine physical activity (e.g., walking or climbing stairs). The three symptoms of migraine are (1) nausea and/or vomiting, (2) both photophobia and phonophobia and (3) typical aura (i.e., visual, sensory, or speech/language) accompanying or within 60 minutes before headache begins. A diary report must simultaneously include at least 2 of the 4 characteristics AND at least 1 of the 3 symptoms in order for a headache day to be counted as a migraine day. The duration constraint is removed if an acute migraine medication is taken that day.

A "probable migraine" day is a headache day of at least █ hours duration for which a diary report must simultaneously include (1) at least 2 of the 4 characteristics and none of the symptoms or (2) exactly 1 of the 4 characteristics and at least 1 of the 3 symptoms. The duration constraint is removed if an acute migraine medication is taken that day.

A "migraine/probable migraine" day is a headache day of at least █ hours duration that is either a migraine day or a probable migraine day. The duration constraint is removed if an acute migraine medication is taken that day. While days of migraine, probable migraine and migraine/probable migraine will be calculated from the data, migraine/probable migraine days are referred to as migraine days in the protocol.

9.3.2.2 Missing Headache Diary Days

Days will only be directly captured as headache-free days or headache days if they are reported on the calendar day or within a 1-day missing-recall window, as defined in Section 9.3.2. Outside such 1-day missing-recall windows, days will only be counted indirectly when pro-rating and/or imputation applies, as indicated in Section 9.3.2.5 and Section 9.3.2.7.

9.3.2.3

Definition of Headache Day, Headache-Free Day and [REDACTED]

A headache day will be defined as a calendar day for which a subject reports at least [REDACTED] hours of headache. The [REDACTED]-hour constraint is removed if an acute headache medication is taken that day. This definition will be altered for sensitivity analyses (to [REDACTED] hours and [REDACTED] minutes of headache).

A migraine day will be defined as a calendar day for which a subject reports at least [REDACTED] hours of migraine. A "probable migraine" day will be defined as a calendar day for which a subject reports at least [REDACTED] hours of a probable migraine. The [REDACTED]-hour constraint is removed if an acute migraine medication is taken that day. A "migraine/probable migraine" day will be defined as a day that is a migraine and/or probable migraine day.

A single headache day will be counted regardless of the number of headache attacks during that day. This applies separately to all types of headache days (e.g., headache days, migraine days, probable migraine days and migraine/probable migraine days).

For headache days of 1 or more total hours, a headache-free day is defined as a calendar day with total hours of headache recorded in the headache diary as 0 or less than 1 total hour without headache medication use, or reported as a day without headache. For headache days of any duration, a headache-free day is defined as a calendar day with total hours of headache recorded in the headache diary as 0 or reported as a day without headache. For headache days of [REDACTED] or more total hours, a headache-free day is defined as a calendar day with total hours of headache recorded in the headache diary as 0 or less than [REDACTED] total hours without headache medication use, or reported as a day without headache.

A [REDACTED] [REDACTED]. Calendar days begin at midnight and last until [REDACTED] 11:59 PM (23:59).

9.3.2.4 Missing-Recall Data

During a diary entry, subjects will be queried about total duration of headaches that day and any associated migraine characteristics and symptoms and headache medication. First though, they will be similarly queried about headaches that occurred during the immediately preceding calendar day, which is the missing-recall window.

Suppose that a subject completes e-Diary on Sunday, 12/12/21 and reports a headache duration █ hours with associated characteristics or symptoms. Then the subject doesn't complete the e-Diary again until Wednesday, 12/15/21, and retrospectively reports no headache occurred on Tuesday, 12/14/21 or Wednesday, 12/15/21 prior to completing the e-Diary. In that case, 12/12/21 would be reported a headache day (as the duration of the headache was █ hours or longer on that day), while 12/13/21 would be captured as a missing diary-data day, because it was not in the 1-day missing-recall window. Since no headache involving 12/14/21 was reported when completing the e-Diary, it would be counted as a headache-free day. Then, the subject completes the e-Diary on Thursday, 12/16/21, and recalls a headache started on 12/15/21 and lasted 6 hours and a headache didn't occur on 12/16/21. Thus, 12/15/21 would be counted as a reported headache day. That is, just as the missing-recall day can be captured as headache days, they can also be captured as headache-free days if there is no data that the subject had a headache day of sufficient duration. Similarly, if the subject does not complete the Diary again until Sunday, 12/19/21 and reports that a headache duration lasting 5 hours occurred on Saturday, 12/18/21, in this case, 12/18/21 will be counted as a reported headache day. Thus, the seven-day period from 12/12 through 12/18 includes three headache days, one of which is a directly-reported headache day (12/12) and two of which are missing-recall headache days (12/15 and 12/18). The seven-day period also includes two headache-free days, one of which is a missing-recall headache-free day (12/14) and one of which is a directly-reported headache-free day (12/16). The seven-day period also includes two days with missing data (12/13 and 12/17). The pro-rated and rounded count of headache days for the subject would be $(3/5)*7$ 4 headache days per week and $(3/5)*28$ 17 headache days standardized to a 28-day period, as described in the prorating section below.

9.3.2.5 Prorating

For the monthly counts, if there are at least 14 days for which the subject has reported headache data (for either headache days or headache-free days), but less than 28 days in a diary period, the data will be prorated accordingly and rounded to the nearest whole number. The prorating will be based on the number of days with reported data in that 28-day period.

For example, if there are 24 days with reported data in the third diary period, the day counts will be multiplied by 28/24 and rounded to a whole number. Then, if the subject's counts for the 28-day period included 14 headache days and 10 headache-free days, after prorating by 28/24, the subject's counts for the 28-day period would be 16 headache days and 12 headache-free days.

For the weekly counts, if there are at least 4 days for which the subject has reported headache data (for either headache days or headache-free days), but less than 7 days in a diary period, the day counts will be prorated accordingly and rounded to the nearest whole number. The prorating will be based on the number of days with reported data in that 7-day period.

For example, if there are 5 days with reported data in a given 7-day diary period, the day counts will be multiplied by 28/5 and rounded to a whole number. Then, if the subject's counts for the 7-day period included 2 headache days and 3 headache-free days, after prorating by 28/5, the subject's counts for the 7-day period would be 11 headache days and 17 headache-free days.

9.3.2.6 Truncation

If the baseline period starting with the screening visit and preceding the first injection exceeds 28 days, then the baseline period will only include the last 28 days. For 28-day periods that occur at the end of an injection cycle, the 28 days ending with Day 84 will be counted, unless truncated by an early injection visit; any days beyond Day 84 and prior to re-injection will be in an overflow period that will not be included in efficacy analyses.

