4.2 Visit Windows

For data to be summarized on a per visit basis, the visit windows used for analysis are defined below.

Analysis Visit	Scheduled Visit	Nominal Day (Days Post Injection)	Case Report Form Window (Days Post Injection)	Diary Window (Days Post Injection)
Week -4	Visit 1	-28	Baseline Phase	-28 to -1
Week -4.1	Visit 1.1	n/a	Baseline overflow	< -28
Day 1	Visit 2	0	0	0
Week 4	Visit 3	28	1 to 42	1 to 28
Week 8	Visit 4	56	43 to 70	29 to 56
Week 12	Visit 5	84	> 70	57 to 84
Week 12.1	Visit 5.1	> 84	n/a	> 84
Week 16	Visit 6	28	1 to 42	1 to 28
Week 20	Visit 7	56	43 to 70	29 to 56
Week 24	Visit 8	84	> 70	57 to 84
Week 24.1	Visit 8.1	> 84	n/a	> 84
Week 28	Visit 9	28	1 to 42	1 to 28
Week 32	Visit 10	56	43 to 70	29 to 56
Week 36	Visit 11	84	> 70	57 to 84
Week 36.1	Visit 11.1	> 84	n/a	> 84
Week 40	Visit 12	28	1 to 42	1 to 28
Week 44	Visit 13	56	43 to 70	29 to 56
Week 48/Exit	Visit 14	84	> 70	57 to 84
Week 48.1/Exit	Visit 14.1	> 84	n/a	> 84

Note: Visit windows will be based on the time since the most recent injection (0 represents Day 1; negative value means the number of days prior to randomization, i.e., -1 represents the day prior to randomization (Day 1)).

In the protocol, the screening visit window is Day -35 to Day -28 and all post-randomization visits have a window of ± 3 days. The analysis windows are aligned with, but wider than, those specified by the schedule of visits and procedures in the protocol in order to include in analyses all study data that fall outside of protocol visit windows. In the event that two visits for a subject occur within the same visit window, if values observed on different study days or values are observed on the same study day with different time stamp, the last observation chronologically for each study phase (baseline, double-blind and open-label) will be used. If values are observed on the same study day without time stamp or values are observed on same study day with the same time stamp,

the average value will be used for analysis. For laboratory variables with qualitative values, if it cannot be determined which is most recent, then the worst measurement will be used. This rule will be applied separately for each variable for non-missing data only.

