Diary data will be assigned per the diary window regardless of the actual visit schedule. Specifically, the diaries will be grouped into 28-day periods for baseline determination prior to randomization and for post treatment injection. This includes the baseline period, defined as the last 28 days of the baseline period (Day -28 to Day -1), and diary months will be the 4-week periods relative to the most recent injection (i.e., Days 1-28, 29-56, and 57-84). The third month of a given injection cycle could be truncated early, because it will end the day prior to a subsequent injection cycle, if that subsequent injection occurs prior to Day 85.

Also, some variables are not scheduled to be recorded at all visits. Visit windows for such visits will be concatenated into the next visit window. For example, for variables that are not to be recorded at Week 4 and Week 8, the analysis window for Week 12 will be widened to include the window for Week 4 and Week 8 (i.e., from Day 2 through the day of the Week 12 injection visit).

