9.3.3 Main Analysis of Primary Efficacy Endpoint

The attributes of the estimand corresponding to the primary efficacy objective are summarized in [Table 1](#).

Table 1. Summary of the Estimand Attributes Corresponding to the Primary Efficacy Objective

Estimand Label	Attributes of the Estimand				
	Treatment	Endpoint	Population	Handling of Intercurrent Events	Statistical Summary
Primary	Arm A: Placebo Arm B: BOTOX 155 U Arm C: BOTOX 195 U	Change from baseline in the frequency of monthly migraine days across Months 5 and 6	The Intent-to-Treat (ITT) Population	IE1: Missing data due to study discontinuations will not be imputed and will be handled as MAR with MMRM. IE2: Regardless of whether rescue medications are taken or not, collected data will be included in the analysis. IE3: Subjects who discontinue study treatment due to any reason will have their data collected after discontinuation of study treatment, and collected data will be included in the analysis.	The difference in the change from baseline in the frequency of monthly migraine days across Months 5 and 6 between each BOTOX dose group and placebo

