A mixed model for repeated measures (MMRM) analysis will be used for the primary analysis, using data for baseline and each month of the double-blind, placebo-controlled phase (i.e., months ending with Weeks 4, 8, 12, 16, 20, and 24). The statistical model will include treatment (BOTOX 195 U, BOTOX 155 U, and placebo), month, country, strata of [REDACTED], and treatment group-by-month interaction as fixed effects, with the baseline number of monthly migraine days as a covariate, included as a continuous variable rather than as the binomial stratification variable. Subject and residual errors will be random effects. Model parameters will be estimated using a restricted maximum likelihood method incorporating all observed data during the double-blind phase. Unstructured covariance structure will be used. Toeplitz or compound symmetry may be considered if convergency issues arise for the unstructured covariance structure. The Kenward-Roger approximation will be used to estimate denominator degrees of freedom. Contrasts will be constructed to obtain the average treatment effects across Months 5 and 6 to compare each BOTOX dose (195 U and 155 U) to placebo group. The ITT population will be used for primary and sensitivity analyses. A few subjects (less than 1%) who did not have post-baseline scores will not be included in the primary MMRM due to having missing values for the dependent variable. These subjects will be included in sensitivity analyses and have post-baseline scores imputed as described in Section 9.2. The primary comparisons of interest will be the pairwise comparisons of each BOTOX dose (195 U and 155 U) versus placebo across Months 5 and 6.

Each dose comparison will be analyzed across primary and secondary endpoints in the order described in Section 13.0, using a ranked-order serial gatekeeping approach to control the overall type I (false positive) error rate. For each BOTOX dose versus placebo, each variable/dose pair will be examined for significance only if significance was determined for all variable/dose pairs ranked ahead of it.

A 2-sided test with a p-value ≤ 0.05 will be considered as statistically significant for the treatment group comparisons of each BOTOX dose (BOTOX 195 U and BOTOX 155 U) versus placebo.

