9.3.4 Sensitivity and Supplementary Analyses of the Primary Efficacy Endpoint

A sensitivity analysis will use the same MMRM model after imputation of missing data by the mLOCF rate-change method, which adjusts the most recent observation by the average change since that observation within the same treatment regimen. This method has been chosen for consistency with methods used for the Phase 3 CM studies of BOTOX.

An additional sensitivity analysis will use the same MMRM, after imputation of missing values by the mLOCF rate-change method, but with imputation instead by reversion toward baseline for post-baseline data (including missing and non-missing observed data) after the date of intercurrent events (e.g., took rescue medications, skipped Week 12 injection but staying in the study, exit due to lack of efficacy, due to adverse events or due to lost to follow-up) that could affect the primary endpoint.

In order to examine the sensitivity of the assumption, which relies on a missing at random/missing completely at random missing-data mechanism (MAR/MCAR), a sensitivity analysis will instead impute a subject's missing scores as the average non-missing score across all previous 28-day periods, including baseline, for the subject. This is defined as "reversion toward baseline" imputation. The reason for this adjustment is that such missing scores might be non-ignorable due to a missing not at random mechanism (MNAR) and the mLOCF assumption of continued effect could be misleading for such subjects, especially regarding the placebo component of any improvement from baseline. This sensitivity imputation will likely dampen down the mean improvement from baseline within treatment groups, but the interest will be in how it affects the treatment comparisons. If conclusions about treatment differences using observed data

and the sensitivity imputations are not qualitatively consistent, the reasons will be explored.

Another sensitivity analysis will use the same MMRM model after imputation of missing data by the multiple imputation (MI) method. The missing values of monthly migraine days will be imputed on the 0 to 28 scale by treatment group with 30 imputed datasets, using the fully conditional specification (FCS) method for ordinal data (via SAS® procedure MI with FCS logistic statement). Changes from Baseline will be calculated after imputation of the monthly migraine days.

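### As written, the diary windows give a subject who skips the Week 12 injection but stays in the study no Month 4–6 value, contrary to the stated estimand

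*SAP*

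**What the plan says.** **Windows.** SAP 4.2 states that "Visit windows will be based on the time since the most recent injection" and that "diary months will be the 4-week periods relative to the most recent injection", with three such periods ending at Day 84. Its table puts later diary days in a separate Week 12.1 row. It also says diary days are assigned by these windows whatever visits actually took place. SAP 9.3.2 and 9.3.2.6 add that "any days beyond Day 84 and prior to re-injection will be in an overflow period that will not be included in efficacy analyses". SAP 3.1 and 9.3.1 define Months 5 and 6 as the periods ending 56 and 84 days after the second treatment. The only fallback anchor, in SAP 2.3, is for a subject who is randomized and never treated.

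**Estimand.** In SAP Table 1, IE3 says that subjects who stop study treatment have data collected "after discontinuation of study treatment, and collected data will be included in the analysis". SAP 9.3.3 describes the primary MMRM as "incorporating all observed data during the double-blind phase". Missing the Week 12 treatment is a named intercurrent event in SAP 8.0 and a deviation category in SAP 7.3. Protocol 5.6 keeps subjects who stop study drug at all scheduled visits in order to limit missing data.

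**Sensitivity analyses.** SAP 9.3.4 lists "skipped Week 12 injection but staying in the study" among the events that trigger reversion toward baseline. It applies that imputation to post-baseline data, "including missing and non-missing observed data) after the date of intercurrent events".

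**The concern.** The endpoint definition and the window rules assume that every subject receives a second double-blind injection. The plan itself expects that some will not, and it expects their diaries to continue.

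For those subjects the window rules discard recorded data that the estimand says will be analysed. Their Months 4–6 become missing in the primary MMRM. They are then predicted from the subject's own baseline and Months 1–3, using the pattern seen in subjects who were re-injected. That describes what would have happened with the second injection, not what did happen without it. SAP 9.2 ties missingness to fewer than 14 reported days in a period, yet these subjects may have reported every day.

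The diary-based secondary endpoints inherit the same rule. Questionnaires have a related fault: scores can land in the wrong window, which affects MSQ at Month 6. Two programmers working from this text could also build different primary datasets.

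**Working it through.** **1. The plan's own case, on schedule.** Days are counted from the first injection as day 0, as in the SAP 4.2 table. With the second injection at day 84, the three following 28-day periods end at 84 + 28 = 112, 84 + 56 = 140 and 84 + 84 = 168. These are Weeks 16, 20 and 24, so the table works as intended.

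**2. The same rules for a subject who misses Week 12.** Diary days 1–168:

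| Injections | Months 1–3 | Overflow (> 84) | Months 4, 5, 6 |
|---|---|---|---|
| Day 0 only | 28 days each | 84 (days 85–168) | 0, 0, 0 |
| Day 0 and day 168 | 28 days each | 83 (days 85–167) | 0, 0, 0 in the double-blind phase |

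Zero days is below the 14-day minimum in SAP 9.3.2.5 and 9.3.2.7, so all three months are missing. Months 1–3 and ITT membership are kept.

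In the second row, the Week 24 open-label injection is literally the second study treatment. The periods ending 56 and 84 days after it run from 168 + 29 = 197 to 168 + 84 = 252, which is inside the open-label phase. Only the restriction of the model to double-blind data stops those days being read as Months 5 and 6.

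**3. Do other analyses recover the data?** The mLOCF and multiple-imputation analyses would impute Months 4–6 as missing. Reversion toward baseline overwrites whatever was recorded after the event. None of the three uses the recorded values.

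**4. Questionnaires.** The Week 12 case report form window is open-ended (more than 70 days after injection). With no second injection, visits at days 84, 112, 140 and 168 all fall in it. SAP 4.2 then says "the last observation chronologically for each study phase (baseline, double-blind and open-label) will be used". A Week 24 MSQ or HIT-6 score can therefore replace the Week 12 score and leave Month 6 empty.

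**5. Size.** The documents give no skip rate, and the assumed effect and SD are redacted. Everything below is assumed.

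*Equal skipping at random.* Let a share p of each arm skip, the drug effect be Δ, and a fraction f of it be lost. The treatment-policy effect is Δ(1 − fp). Handling the skippers as missing at random returns Δ. The relative overstatement is fp/(1 − fp).

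| p | All benefit lost (f = 1) | Half lost (f = 0.5) |
|---|---|---|
| 3% | 0.03/0.97 = 3.1% | 0.015/0.985 = 1.5% |
| 5% | 0.05/0.95 = 5.3% | 0.025/0.975 = 2.6% |
| 10% | 0.10/0.90 = 11.1% | 0.05/0.95 = 5.3% |

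A simulation used 1,000,000 subjects per arm, an assumed SD of 3.5 and correlation of 0.6, with Months 5–6 predicted from Months 1–3. It gave 3.1%, 5.2% and 11.5% for full loss and 1.6%, 2.5% and 5.1% for half loss, in agreement within simulation error. At p = 1% with full loss the formula gives 0.01/0.99 = 1.0%.

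*Unequal skipping.* Assume a mean reduction of 4 days on BOTOX and 3 on placebo, with all of it lost after skipping. The treatment-policy effect is 4(1 − pT) − 3(1 − pP) = 1 − (4pT − 3pP), where pT and pP are the skip shares on BOTOX and placebo. The missing-at-random result is 1.00.
- 5% BOTOX, 3% placebo: 1 − (0.20 − 0.09) = 0.89, and 1/0.89 is an overstatement of 12.4%.
- 3% BOTOX, 5% placebo: 1 − (0.12 − 0.15) = 1.03, and 1/1.03 is an understatement of 2.9%.

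**The case against.** The strongest reply is that the intent is plain. IE3 includes post-treatment data, SAP 7.3 tracks these subjects, and SAP 9.3.4 presupposes observed values after a skip. On that view a derivation sentence is missing, and harm follows only if a programmer applies the windows against the estimand. The intent is indeed clear. But the windows are stated rules, and SAP 4.2 rules out falling back on the visit schedule, so following the text exactly gives the wrong dataset.

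Three textual points have some force.
- The overflow sentence speaks of days before re-injection, so its application to a subject never re-injected is unclear. The Day 84 limit and the second-treatment definition give the same result without it, and the sentence fits exactly a subject next injected at Week 24.
- IE3 concerns stopping treatment. It does not clearly cover a subject who misses Week 12 and resumes at Week 24. For that subject the conflict is with SAP 8.0 and 9.3.4.
- The 9.3.3 phrase may mean all observed monthly scores, not every diary day. That makes it the weaker of the two conflicts.

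The reversion-toward-baseline analysis does cover these subjects and lowers the risk of an unnoticed distortion. It does not deliver the treatment-policy estimate. The size may also be slight: 1% skipping is about 3 of 259 subjects per arm.

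**Conclusion.** The concern holds. Read literally, the SAP leaves skip-and-stay subjects with no double-blind Month 4–6 diary value, although it says their data will be used and although it foresees the event. This is a stated rule that gives a wrong result, and it should be fixed.

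Confidence in the gap is high. Its consequence cannot be sized from the documents, because the skip rate, the loss of effect and the split between arms are all assumptions. With equal skipping of 3% to 10%, the overstatement runs from 1.5% (half the benefit lost, 3% skipping) to 11.1% (all lost, 10% skipping). With unequal skipping the sign can go either way. The impact on the primary result is small unless skipping is common or differs by arm.

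**What to change.** Amend SAP 3.1, 4.2, 9.3.1, 9.3.2 and 9.3.2.6 to state the following.

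1. The second study treatment means the second double-blind injection. This stops a Week 24 open-label injection from counting as the second.
2. For a subject with no second double-blind injection before the Week 24 visit, Months 4, 5 and 6 are Days 85–112, 113–140 and 141–168 after the first injection, ending the day before any open-label injection. An injection on Day 168 leaves 27 days in Month 6, which the existing prorating handles.
3. For these subjects, cap the Week 12 case report form window and continue the table's midpoints (42 and 70, then 98, 126 and 154): Week 12 is Days 71–98, Week 16 is 99–126, Week 20 is 127–154, and Week 24 is Day 155 through the Week 24 visit, before any open-label injection. Simply restarting the table at a nominal Day 84 would put a Week 12 visit on Day 87, which the ±3-day window allows, into Week 16.
4. After the first injection, the overflow exclusion applies only to the gap before a delayed second double-blind injection. Later cycles are unchanged.

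Item 2 alone repairs Months 4–6 if the overflow rule is adjusted to match. Item 3 is needed for MSQ and HIT-6. The cost is a few sentences, one derived anchor date and a short window table for this subset. These are analysis windows only: no new data are needed and no treatment rule changes.
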